Protocol for non-interventional studies based on existing data

Document Number:	C20330622
BI Study Number:	1218.182
BI Investigational Product(s):	Tradjenta
Title:	Real world glycemc effectiveness of linagliptin (Tradjenta®) among type 2 diabetes mellitus adults by age and renal function.
Protocol version identifier:	1.0
Date of last version of protocol:	20 October 2017
PASS:	No
EU PAS register number:	Not applicable
Active substance:	Linagliptin
Medicinal product:	Tradjenta
Product reference:	N/A
Procedure number:	N/A
Joint PASS:	No
Research question and objectives:	
The primary study objective is to:
 
 Describe change in HbA1c among adults with T2DM within 60 to 180 days following initiation of linagliptin across pre-defined age and renal function categories. Age categories will be defined as: 40 to 54 years, 55 to 64 years, 65 to 74 years, and ≥ 75 years. Renal function categories will be defined based on eGFR as: <30 ml/min/1.73m², 30 to 44 ml/min/1.73m², 45 to 59 ml/min/1.73m², 60 to 89 ml/min/1.73m², and ≥ 90 ml/min/1.73m². 
The secondary study objectives are to:
 
 Compare change in HbA1c among adults with T2DM within 60 to 180 days following initiation of linagliptin across pre-defined age and renal function categories. Compare the proportion of adults with T2DM who achieve HbA1c $< 7.0\%$ within 60 to 180 days following initiation of linagliptin across the pre-defined age and renal function categories.

Country(-ies) of study:	USA
Author:	
Marketing authorisation holder(s):	Boehringer Ingelheim International GmbH [name] [name]
In case of PASS, add: <EU-QPV>	Not Applicable
In case of PASS, add: <Signature of EU-QPV>	Not Applicable
MAH contact person:	Not Applicable
Date:	20OCT17

Page 1 of 42

Proprietary confidential information
 © 2017 Boehringer Ingelheim International GmbH or one or more of its affiliated companies. All rights reserved.
 This document may not - in full or in part - be passed on, reproduced, published or otherwise used without prior written permission

2. LIST OF ABBREVIATIONS

CI	Confidence interval
CKD-EPI	Chronic Kidney Disease Epidemiology Collaboration
DPP-4	Dipeptidyl peptidase-4
eGFR	Estimated glomerular filtration rate
EHR	Electronic health record
GLP-1RA	Glucagon-like peptide-1 receptor agonist
HbA1c	Glycosylated hemoglobin
IRB	Institutional Review Board
Scr	Serum creatinine
SGLT2	Sodium-glucose co-transporter 2
T2DM	Type 2 diabetes mellitus
TZD	Thiazolidinediones

3. RESPONSIBLE PARTIES

4. ABSTRACT

Name of company: Boehringer Ingelheim			
Name of finished medicinal product: Tradjenta			
Name of active ingredient: Linagliptin			
Protocol date: 20-OCT-2017	Study number: 1218.182	Version/Revision: 1.0	Version/Revision date:
Title of study:	Real world glycemc effectiveness of linagliptin (Tradjenta) among type 2 diabetes mellitus adults by age and renal function		
Rationale and background:	
Patients with type 2 diabetes mellitus (T2DM) have progressive decline in renal function and this decline in function is greater than age-related decline in patients without diabetes. Selection of glucose lowering agents is often affected by the level of renal function. Dipeptidyl peptidase-4 (DPP-4) inhibitors are approved to treat hyperglycemia among adults with T2DM with a wide range of renal function. In contrast to most other DPP-4 inhibitors, linagliptin does not require dose adjustment as renal function declines. Without further requirement of dose adjustment, linagliptin affords simplicity for chronic management of HbA1c.
 
Current literature indicate that decline in renal function is also associated with glycemc control, hypertension, albuminuria and dyslipidemia. However, there is limited evidence about the real world effectiveness and safety of linagliptin across different age and renal functions among adults with T2DM.
 
For better management of hyperglycemia it is pertinent to understand the glycemc effectiveness of linagliptin among adults with T2DM with varying age and renal function who are treated in the real world setting. With a potentially larger sample size, it is possible to compare the glycemc effectiveness of linagliptin across the range of ages and renal function.
 
The aim of the current study is to compare real world glycemc effectiveness across a range of ages and renal function among adults with T2DM who are initiated on linagliptin.
		
Research question and objectives:	
The primary study objective is to:
 
 Describe change in HbA1c among adults with T2DM within 60 to 180 days following initiation of linagliptin across pre-defined age and renal function categories. Age categories will be defined as: 40 to 54 years, 55 to 64 years, 65 to 74 years, and ≥ 75 years. Renal function categories will 		

	
be defined based on eGFR as: <30 ml/min/1.73m², 30 to 44 ml/min/1.73m², 45 to 59 ml/min/1.73m², 60 to 89 ml/min/1.73m², and ≥ 90 ml/min/1.73m².
 
The secondary study objectives are to:
 
• Compare change in HbA1c among adults with T2DM within 60 to 180 days following initiation of linagliptin across pre-defined age and renal function categories.• Compare the proportion of adults with T2DM who achieve HbA1c $< 7.0\%$ within 60 to 180 days following initiation of linagliptin across the pre-defined age and renal function categories.
--	---

Study design:	Non-interventional study based on existing data
Population:	Patients with T2DM newly initiated on linagliptin, in the Optum electronic health record (EHR) database, aged 40 and older, and with HbA1c values during the both the 180 days before and the 60 to 180 days after starting linagliptin
Variables:	
Outcomes:
 
 • Primary: Change in HbA1c within 60 to 180 days after initiation of linagliptin • Secondary: HbA1c goal (< 7.0%) attainment during the 60 to 180 days after initiation of linagliptin 
Covariates:
 
 • Age categories: 40 to 54 years, 55 to 64 years, 65 to 74 years, and ≥ 75 years • Sex • Race • Ethnicity • Geographic region • Pre-index comorbidity score • Pre-index HbA1c value • Pre-index renal function categories (based on the eGFR): <30 ml/min/1.73m², 30 to 44 ml/min/1.73m², 45 to 59 ml/min/1.73m², 60 to 89 ml/min/1.73m², and ≥ 90 ml/min/1.73m²
Data sources:	Optum electronic health record (EHR) data
Study size:	
This study is exploratory and not characterized with a priori hypotheses. All patients identified in the data that meet the inclusion criteria and do not meet the exclusion criteria will be included in the study population.
 
A sample size calculation was conducted to determine the minimum number of patients that would be required to detect a change in HbA1c of at least 0.5% among the cohort groups. Based on previously published studies, it was assumed that the standard deviation for the 24-week mean change in HbA1c from baseline could range between 1.2 and 1.5. Assuming a SD of 1.2 for the change in HbA1c, at least 92 patients would be needed in each of the two smallest groups of the cohort of interest (e.g., age, renal function, age by renal function) in order to have 80% power to detect a mean difference in HbA1c of at least 0.5% using a two-sided test at an alpha of 0.05. If the standard deviation for the change in HbA1c is 1.5, then 143 patients would be needed in each of the two smallest groups.

Data analysis:	
Primary analysis
 
All study variables, including pre-index and outcome measures, will be analyzed descriptively. Pre-index and outcome measures will be reported for the overall study population as well as stratified by predefined subgroups of patients.
 
The following stratifications will be conducted among the overall study population:

	
 • By age categories defined as 40 to 54 years, 55 to 64 years, 65 to 74 years, and ≥ 75 years • By renal function categories (based on eGFR) defined as: < 30 ml/min/1.73m², 30 to 44 ml/min/1.73m², 45 to 59 ml/min/1.73m², 60 to 89 ml/min/1.73 m², ≥ 90 ml/min/1.73m², and not available • By race defined as White, African American, Asian, or Other/Unknown 
Secondary analysis
 
Comparisons of pre-index characteristics and outcome measures will be provided, and appropriate tests will be used based on the distribution of the measure. Continuous measures will be compared using t-tests and categorical measures will be compared using chi-square tests. P-values and 95% confidence intervals will be reported. Reported p-values will not be adjusted for multiple comparisons.
 
In addition to the descriptive analyses described above, multivariable modelling will be considered to assess change in HbA1c, controlling for an a priori list of covariates. The use of multivariable modelling will be dependent on having robust sample size distribution across age and eGFR categories.

Milestones:
	
Protocol Completion Data Extraction, Preparation & QA Data Analysis Final Report

5. AMENDMENTS AND UPDATES

None

6. MILESTONES

Milestone	Planned Date
Optum to deliver first draft of protocol	14 July 2017
BIPI to provide comments on first draft of protocol	28 July 2017
Optum to deliver second draft of protocol	11 August 2017
BI to provide comments on second draft of protocol	25 August 2017
Optum to deliver final protocol	01 September 2017
BIPI approval of final protocol	19 October 2017
Optum to deliver count of qualifying patients in table format following delivery of final protocol	30 November 2017
Optum to deliver descriptive analysis results tables	12 January 2018
Optum to deliver multivariable model results tables	2 February 2018
Optum to deliver draft report	2 March 2018
BIPI to provide comments following delivery of draft report	16 March 2018
Optum to deliver final report	30 March 2018

7. RATIONALE AND BACKGROUND

Patients with type 2 diabetes mellitus (T2DM) have progressive decline in renal function and this decline in function is greater than age-related decline in patients without diabetes (1-4). Selection of glucose lowering agents is often affected by the level of renal function. Dipeptidyl peptidase-4 (DPP-4) inhibitors are approved to treat hyperglycemia among adults with T2DM with a wide range of renal function. In contrast to most other DPP-4 inhibitors (5), linagliptin does not require dose adjustment as renal function declines. Without further requirement of dose adjustment, linagliptin affords simplicity for chronic management of HbA1c.

Current literature indicate that decline in renal function is also associated with glycemic control, hypertension, albuminuria and dyslipidemia (9-11). However, there is limited evidence about the real world effectiveness and safety of linagliptin across different age and renal functions among adults with T2DM.

Data from clinical studies demonstrate that the expected reduction in HbA1c should be similar across the range of ages, but direct comparisons with younger patients are not available. Barnett et al reported on 238 patients aged 70 or older randomized to linagliptin 5 mg daily (n = 160) or placebo (n=78). The placebo adjusted mean difference in HbA1c after 24 weeks was -0.64% (95% CI -0.81 to -0.48) (12). Inzucchi et al reported on 247 patients aged 70 or older randomized to linagliptin (n = 126) or placebo (n = 121) added to basal insulin (13). The placebo adjusted mean difference in HbA1c after 24 weeks was -0.77 (94% CI -0.95 to -0.59). These values are consistent with other studies of linagliptin, but do not provide direct comparison data with younger patients.

Limited data from studies evaluating linagliptin in patients with renal impairment suggest that glycemic control is maintained across different levels of renal function. Groop et al analyzed data from three 24 week linagliptin clinical trials (n = 2,262) in which data from 2,143 subjects were available to calculate renal function using the Modified Diet Renal Disease (MDRD) equation (14). Subjects were divided by renal function into normal renal function (eGFR \geq 90 ml/min/1.73 m²), mild renal impairment (eGFR 60 to < 90 ml/min/1.73 m²) and moderate renal impairment (eGFR 30 to < 60 ml/min/1.73m²). Distribution of subjects assigned to linagliptin vs. placebo by renal function category was as follows: 1) normal renal function: 870 linagliptin subjects and 342 placebo subjects; 2) mild renal function: 620 linagliptin subjects and 218 placebo subjects; and 3) moderate renal function: 68 linagliptin subjects and 25 placebo subjects. The reduction in HbA1c was consistent across ranges of renal function. However, the number of patients in the moderate renal dysfunction category was quite small, so there is greater uncertainty about the magnitude of the HbA1c reduction in this group. These observations support the current proposal to demonstrate comparable effects in glycemic effectiveness across the range of renal function categories and provide more information in patients with low renal function especially in patients with eGFR < 45 ml/min/1.73 m².

For better management of hyperglycemia it is pertinent to understand the glycemic effectiveness of linagliptin among adults with T2DM with varying age and renal function who are treated in the real world setting. With a potentially larger sample size, it is possible to compare the glycemic effectiveness of linagliptin across the range of ages and renal function.

The aim of the current study is to compare real world glycemic effectiveness across a range of ages and renal function among adults with T2DM who are initiated on linagliptin.

8. RESEARCH QUESTION AND OBJECTIVES

The purpose of this study is to assess glycemic control among adults with T2DM during the 60 to 180 days following initiation of linagliptin.

The primary study objective is to:

- Describe change in HbA1c among adults with T2DM within the 60 to 180 days following initiation of linagliptin across pre-defined age and renal function categories. Age categories will be defined as: 40 to 54 years, 55 to 64 years, 65 to 74 years, and ≥ 75 years. Renal function categories will be defined based on eGFR as: <30 ml/min/1.73m², 30 to 44 ml/min/1.73m², 45 to 59 ml/min/1.73m², 60 to 89 ml/min/1.73m², and ≥ 90 ml/min/1.73m².

The secondary study objectives are to:

- Compare change in HbA1c among adults with T2DM within 60 to 180 days following initiation of linagliptin across pre-defined age and renal function categories.
- Compare the proportion of adults with T2DM who achieve HbA1c $< 7.0\%$ within 60 to 180 days following initiation of linagliptin across the pre-defined age and renal function categories.

9. RESEARCH METHODS

9.1 STUDY DESIGN

This will be a non-interventional cohort study using existing data from patients in the Optum Clinical Database which contains electronic health record (EHR) data from providers across the United States.

Real-world EHR data will be used to determine whether there is comparable effectiveness of linagliptin 5 mg daily on glycemic effectiveness as determined by the change in HbA1c and the percentage of patients achieving an HbA1c goal of < 7.0% during the 60 to 180 days after initiation of linagliptin across a range of age and renal function categories.

[figure not shown]

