9.5 STUDY SIZE

This study is exploratory and not characterized with *a priori* hypotheses. All patients identified in the data that meet the inclusion criteria and do not meet the exclusion criteria will be included in the study population.

A sample size calculation was conducted to determine the minimum number of patients that would be required to detect a change in HbA1c of at least 0.5% among the cohort groups. Based on previously published studies, it was assumed that the standard deviation for the 24-

week mean change in HbA1c from baseline could range between 1.2 (based on the placebo adjusted value in the MARLINA-T2D trial (20)) and 1.5 (based on retrospective studies of diabetes treatments using electronic medical record data from across the United States (21)). Assuming a SD of 1.2 for the change in HbA1c, at least 92 patients would be needed in each of the two smallest groups of the cohort of interest (e.g., age, renal function, age by renal function) in order to have 80% power to detect a mean difference in HbA1c of at least 0.5% using a two-sided test at an alpha of 0.05. If the standard deviation for the change in HbA1c is 1.5, then 143 patients would be needed in each of the two smallest groups.

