9.7 DATA ANALYSIS

9.7.1 Feasibility Assessment

Feasibility analyses will include determinations of the number of patients in each potential category of age and renal function. Some cells may be too small (e.g. eGFR 30 to 44 ml/min/1.73m²), but as long as most of the key groups have sufficient numbers (as described in Section 9.5 Study Size) of patients this will not detract from the overall results. The number of AA individuals will not be as large as the full data set and as such some of the age and eGFR groups will be much smaller than for the whole group. Since the AA subgroup analysis is exploratory, having some small groups will not significantly limit the overall clinical interpretation even if statistical comparability cannot be confirmed.

Optum conducted a feasibility analysis using data from the Optum EHR database. There were 63,499 patients identified with a written prescription for linagliptin between January 1, 2012 and June 30, 2016. After excluding patients without data available for a six-month pre-index period, patients with a prescription for linagliptin or other DPP-4 inhibitor, and patients less than 40 years of age, the patient count was reduced to 38,868 patients.

A total of 16,566 patients had at least one HbA1c result during the six-month period prior to the index date and at least one HbA1c result during the six-month period after the index date. Of these, 16,566 adult patients were newly initiated on linagliptin with baseline and follow-up HbA1c results, race/ethnicity was available in 15,289 patients, a serum creatinine value was available for 15,130 patients, and both race/ethnicity and serum creatinine were available for 13,962 patients.

Among the 13,962 patients meeting the criteria and with a baseline serum creatinine, the smallest age group cell (40-54 years) had more than 2,500 patients and the cell with age > 75 years (which is of special interest in this protocol) had more than 3,000 patients. Thus, for the primary end point to assess HbA1c across age ranges, each category is of sufficient size to conduct this study.

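### Section 9.7.3 describes no baseline-adjusted comparison of HbA1c goal attainment, a formal secondary objective, and the plan's comparability wording goes beyond what its difference tests can show

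*Combined protocol and SAP*

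**What the plan says.** **Objectives.** Section 8 has a primary objective to describe HbA1c change across age and renal categories. Its secondary objectives are to compare that change and, separately, to compare goal attainment: "Compare the proportion of adults with T2DM who achieve HbA1c" below 7.0%. Section 9.3.2.2 defines attainment as any value below 7.0% in the 60 to 180 day window.

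**Analysis.** Section 9.7.3 compares continuous measures with t-tests and categorical measures with chi-square tests. It reports 95% CIs and p-values without multiplicity adjustment. A multivariable model is to be considered, if cell sizes allow, for change in HbA1c (OLS, or MMRM if most patients have repeated values). Its covariates include pre-index HbA1c. Goal attainment is not named as an outcome of any model there.

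**Baseline.** Section 9.9 says that groups may differ in baseline HbA1c and that a higher baseline goes with a larger fall.

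**Comparability wording.** Section 9.1 says: "Real-world EHR data will be used to determine whether there is comparable effectiveness of linagliptin 5 mg daily on glycemic effectiveness". Section 7 says: "These observations support the current proposal to demonstrate comparable effects in glycemic effectiveness across the range of renal function categories". Section 9.7.1, on the African American subgroup, says: "having some small groups will not significantly limit the overall clinical interpretation even if statistical comparability cannot be confirmed". Section 9.9 also refers to a claim of comparable effectiveness across renal function.

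**Size.** Section 9.5 says "This study is exploratory and not characterized with" a priori hypotheses. Its 92 or 143 patients per group are set "in order to have 80% power to detect a mean difference in HbA1c of at least 0.5% using a two-sided test". On feasibility counts, Section 9.7.1 reports that "the smallest age group cell (40-54 years) had more than 2,500 patients" and that the cell above 75 years had more than 3,000.

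**The concern.** Goal attainment is a threshold outcome. A group that starts at a higher HbA1c will have fewer patients below 7.0% at follow-up unless the whole starting gap closes. The chi-square test cannot separate that from a difference in how well linagliptin works. The plan handles the problem for HbA1c change by putting pre-index HbA1c in the model, but describes nothing equivalent for attainment. With age groups in the thousands, a modest baseline gap can give a significant attainment result that says little about effectiveness.

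The second matter is interpretive. A test of difference does not answer whether groups are comparable. In a small low-eGFR cell, a non-significant result leaves room for a sizeable difference. In a large age cell, a trivial difference can be significant. With no rule stated, either result could be misread against the aim in Section 9.1.

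**Working it through.** **1. The plan's sample size.** Inputs from Section 9.5: difference 0.5%, SD 1.2 or 1.5, two-sided alpha 0.05, power 80%.

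n per group = 2 × [SD × (1.960 + 0.842) / 0.5]²

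- SD 1.2: 90.4, rounded up to 91; the t-test version gives 91.4, so 92.
- SD 1.5: 141.3, rounded up to 142; the t-test version gives 142.2, so 143.

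Both stated figures reproduce exactly as a two-sided test of difference. The 0.5% is a difference to detect, not a margin.

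**2. What non-significance means for HbA1c change.** SE = SD × √(1/n₁ + 1/n₂), and P(non-significant) = Φ(1.96 − d/SE) − Φ(−1.96 − d/SE).

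- 92 versus 92, SD 1.2: SE 0.177, 95% CI half-width 0.35%. For a true d of 0.3%, P = 0.604.
- 143 versus 143, SD 1.5: SE 0.177, half-width 0.35%. For a true d of 0.3%, P = 0.606.
- The same minimum cells against an assumed reference group of 500 to 2,500: P = 0.35 to 0.44.
- 2,500 versus 3,000: SE 0.0325 (SD 1.2) or 0.0406 (SD 1.5). An observed difference of 1.96 × SE, that is 0.064% or 0.080%, reaches p<0.05.

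**3. Goal attainment with no difference in effectiveness.** The documents give no follow-up distribution and no baseline gap, so these inputs are assumptions: follow-up HbA1c normal with mean 7.2, 7.5 or 7.8% and SD 1.2, 1.5 or 1.8; baseline gap 0.3%. The part of the gap left at follow-up is varied. The group sizes 2,500 and 3,000 are the lower bounds in Section 9.7.1.

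Share at goal = Φ((7.0 − mean)/SD). The second group's mean is higher by the retained gap.

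Worked case, mean 7.5, SD 1.5, half the gap retained (0.15%):

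- Group 1: Φ(−0.5/1.5) = 0.369. Group 2: Φ(−0.65/1.5) = 0.332. Shift 3.7 points.
- Pooled share 0.349; SE = √[0.349 × 0.651 × (1/2,500 + 1/3,000)] = 0.0129.
- z = 0.0371/0.0129 = 2.87, so power is about Φ(2.87 − 1.96) = 0.82.

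Over all nine combinations of mean and SD:

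| Share of 0.3% gap retained | Shift in attainment (points) | Chi-square significant |
|---|---|---|
| Quarter (0.075%) | 1.5 to 2.4 | 22 to 45% |
| Half (0.15%) | 3.0 to 4.9 | 65 to 95% |
| All (0.30%) | 5.8 to 9.5 | over 99% |

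The last row means equal HbA1c change in both groups. Section 9.9 says larger falls go with higher baselines, so that row is an upper bound for a 0.3% gap and not the expected case.

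**The case against.** **The text may not be the whole plan.** Section 9.2.3 cites a sensitivity analysis in Section 9.7.4.4, which is neither in the body nor in the contents list. Section 12 and Appendix C refer to a separate analysis plan that is not part of the text available. An adjusted attainment model could be described there. This stands, and it limits the point to Section 9.7.3. The documents mention Section 9.7.4.4 only for medication added during follow-up, and the analysis plan only for table shells, so nothing indicates that such a model exists.

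**The comparability issue is largely wording.** The formal objectives are to describe and to compare, the study is called exploratory, 95% CIs will be reported, and Section 9.9 openly allows for a non-comparable result. This also stands. A reader might infer that the plan must have an equivalence margin, or that the primary analysis fails without one. The documents do not support that: the primary analysis is descriptive and unaffected. A margin would also need a reference category, which the fallback in Section 9.7.3 to continuous age or eGFR could remove.

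**The attainment figures rest on assumed inputs.** True. The calculation also uses one follow-up value per patient, whereas the plan counts any value below 7.0% in the window. The feasibility counts precede several of the exclusions. The figures show that the distortion can matter, not how large it will be. The reason for adjustment is in Section 9.9 itself and does not depend on them.

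**Conclusion.** The point holds, within limits. In Section 9.7.3 as available, a formal secondary objective has only an unadjusted test, while the companion outcome has a planned model that includes pre-index HbA1c. On the stated assumptions, a 0.3% baseline gap that is a quarter to a half retained produces a shift of about 1.5 to 4.9 points without any difference in effectiveness. At 2,500 versus 3,000 patients that shift is significant in about 22 to 95% of studies. A reader might take the 5.8 to 9.5 point figure as the likely size, but it needs the whole gap to persist, which Section 9.9 makes unlikely.

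The comparability wording is a secondary point. At the planned minimum cell sizes, a true 0.3% difference in HbA1c change is missed about 60% of the time, so non-significance there cannot be read as comparable effectiveness. The documents give no eGFR cell counts, so actual cells may be larger. The sample size itself is correctly calculated, but for detecting a difference.

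**What to change.** **Goal attainment.** Add to Section 9.7.3 a regression for goal attainment adjusted for pre-index HbA1c and the other covariates listed there. Use the same age and eGFR coding as the HbA1c-change model, including its fallbacks. Report adjusted group contrasts with 95% CIs as the main comparison for this objective, and keep the chi-square results as descriptive. If the analysis plan already contains such a model, a cross-reference in Section 9.7.3 is enough.

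**Comparability.** Align the wording in Sections 7, 9.1, 9.7.1 and 9.9 with the describe and compare objectives. Report estimates with CIs, and state before results are seen that a non-significant p-value will not be read as comparability. A pre-specified margin is optional.

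**Cost.** One more model on covariates already planned, and a few sentences of rewording. No new data are needed.
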